#### 10.4 Subgroup analyses

Any subgroup analyses will be post-hoc. Based on specified hypothesis the participants will be sub grouped with respect to its baseline characteristics.

#### 10.5 Adjusted analysis

We intend to perform a responder analysis within the accelerated weaning group to identify predictors of weaning success/failure.

#### 10.6 Interim analysis and criteria for premature termination of the trial

No routine interim analysis is planned. However, if a substantial difference in survival arises, the DMC will consider performing an interim survival analysis. Decisions on premature termination of the trial will be taken in accordance with the Haybittle-Peto boundary,

ISRCTN: 64639614 IRAS: 313485 CPMS: 53277

considering a p-value of less than 0.001 as "significant" and the likely impact on future practice. The DMC are not solely bound by this recommendation in regard to survival alone, but will undertake an holistic assessment of the trial and report to the TSC.

#### 10.7 Participant population

Participants will be aged 35 years and over, admitted to hospital with exacerbation of COPD. They will have been treated with NIV for AHRF, have a low or medium risk NIV Outcomes score, and have met the eligibility criteria to be randomised and wean from ventilation. Patients will not be excluded for any equality and diversity reasons, (e.g. ethnic background, socioeconomic status), and we will support recruitment of people from diverse backgrounds (e.g. those with language barriers). We will monitor recruitment at individual sites, and discuss any problems with recruitment at Trial Management Group meetings.

#### 10.8 Procedure(s) to account for loss to follow-up or missing

We consider the tolerable level of loss to follow-up or missing is less than 10%. Every effort will be made to minimise missing baseline and outcome data (data verification and validation). Standard approaches will be used to detect patterns in missing data. The level and pattern of the missing data in the baseline variables and outcomes will be established by forming appropriate tables and the likely causes of any missing data will be investigated. This information will be used to determine whether the level and type of missing data has the potential to introduce bias into the analysis results for the proposed statistical methods, or substantially reduce the precision of estimates related to treatment effects. Data quality will be closely monitored and we will perform on site data verification and validation for all outcome measures and expect missing data rates to be low. In case of substantive proportion of missing data, a multiple imputation will be performed, with missing data assumed to be missing at random, to create at least five data sets (depending on missing data per sites) using the chained equation (MICE Algorithm). In addition, we will conduct sensitivity analysis to examine the robustness of the findings (hypothesis testing or estimates).

#### 10.9 Economic evaluation

An embedded economic evaluation will estimate the cost effectiveness (CE) and cost utility (CU) of the accelerated weaning protocol in comparison with standard care for NIV weaning from an NHS perspective. Costs of the protocols, resource use and associated costs will be estimated during the index admission for ECOPD up until discharge from electronic hospital records, and will include critical care, respiratory support unit and general ward length of stay (LOS). In addition, NHS resource use (primary, secondary and community care) and associated costs will be captured up until 90 days post-randomisation, triangulated from a number of sources. At discharge, participants will be given a heath resource diary to record events related to any COPD and non-COPD associated treatment they receive during the study. The diary is divided into four sections: (i) GP resources; (ii) hospital outpatient resources; (iii) accident and emergency (A&E) resources; and (iv) hospital admission resource used. Entries will include who they saw, where they saw them, whether it was emergency or routine, the reason for any A&E visit and length of any hospital stay.

Participants will be contacted via telephone by a researcher at 30 and 90 days post randomisation to complete a proforma which captures use of NHS services detailed in patient diaries from discharge. These estimates will be triangulated with electronic NHS records to check for accuracy. Appropriate unit costs will be applied to the NHS resources used by each trial participant. Similarly, the costs of the intervention will be estimated by

ISRCTN: 64639614 IRAS: 313485 CPMS: 53277

calculating the average cost of providing the intervention to patients. EQ-5D -5L QALYs will be estimated using the area under the curve approach and will be adjusted by time. Cost and effectiveness (utility) will be analysed as intention to treat and missing data will be imputed using multiple imputation. In the deterministic analysis, mean values of cost and effectiveness (utility), derived from generalized linear model adjusting for potential confounders, will be used as a representative value for calculating ICER (incremental cost-effectiveness ratio).

Uncertainty around estimates of CE and CU will be explored using cost effectiveness/utility acceptability curves (CEACs), which express uncertainty of outcome as a function of willingness to pay for a unit of outcome.

We will utilise findings from the economic evaluation and the evidence-base to provide a return on investment tool that organisations can utilise to assess value for money within local contexts; ultimately strengthening the alignment between data analysis and decision-making processes. The return on investment is the benefit minus the cost expressed as a proportion of the cost. This spreadsheet-based toolkit will estimate the costs and consequences of accelerated weaning according to local characteristics and assumptions, such as prevalence of disease and anticipated demand for the intervention.

### 11. Data Management

#### 11.1 Data collection tools and source document identification

Data for each participant will be collected on a source document worksheet designed for the trial.

#### 11.2 Data handling and record keeping

All study data will be entered onto a secure (N3 network with encryption) online database (REDCap) with integral data validation functionality. Trial participants will be identified by a unique trial specific participant code in the database, so that name and identifying data will be blinded to the statistician and health economist. On site data validation will be performed for all outcome indices for each participant. The database will have a security system to protect against unauthorised access and levels of access for sites, and scheduled weekly data back up, so that data is protected. We will maintain an audit trail of all data changes, to ensure that no data is deleted.

All study documents will be stored safely in confidential conditions at site. Personal data will be securely destroyed on completion of all data queries and database lock. Research data generated by the trial and its process evaluation will be stored for 3 years.

Data will be handled and stored in accordance with the 2018 General Data Protection Regulation (GDPR).

[name] and [name] are responsible for data collection, recording and quality.

#### 11.3 Access to Data

Direct access will be granted to the CI and PI at the host institution (Northumbria Healthcare) for monitoring and/or audit of the study to ensure compliance with regulations.

NIVOW\_Protocol v1.2 ISRCTN: 64639614

ISRCTN: 64639614 IRAS: 313485 CPMS: 53277

#### 11.4 Archiving

Each site will be responsible for storing and archiving their own study data. Archiving will be maintained for a minimum of 3 years after completion of the trial.

#### 12. Monitoring, Audit and Inspection

The Data Monitoring Committee (DMC) will report to the Trial Steering Committee (TSC). The TSC will include a patient representative. Meetings will occur 6-12 monthly, with independent Chairs and membership in line with NIHR guidance. The Trial Management Group, chaired by the CI, will meet monthly.

Remote and on-site data verification and validation, including participant eligibility and all primary and secondary outcome data, will be performed. The CI reserves the right to review all processes at all sites. Processes reviewed can relate to participant enrolment, consent, eligibility, and allocation to trial groups; adherence to trial interventions and policies to protect participants, including reporting of harm and completeness, accuracy, and timeliness of data collection.

Sites will be expected to assist the sponsor in monitoring the trial. This will include hosting site visits, providing information for remote monitoring or data validation or verification, or putting procedures in place to monitor the trial internally.

Site monitoring visits will include an early initial visit after participant recruitment, and subsequently scheduled every 6 – 12 months using a risk-based approach that focuses, for example, on sites that have the highest enrolment rates, large numbers of withdrawals, or atypical (low or high) numbers of reported adverse events.

#### 13. Ethical and Regulatory Considerations

### 13.1 Research Ethics Committee (REC) Review and Reports

Before the start of the trial, approval will be sought from a REC for the trial protocol, informed consent forms and other relevant documents e.g. GP information letters.

Substantial amendments that require review by REC will not be implemented until the REC grants a favourable opinion for the trial (note that amendments may also need to be reviewed and accepted by the MHRA and/or NHS R&D departments before they can be implemented in practice at sites).

All correspondence with the REC will be retained in the Trial Master File/Investigator Site File.

An annual progress report (APR) will be submitted to the REC within 30 days of the anniversary date on which the favourable opinion was given, and annually until the trial is declared ended.

It is the Chief Investigator's responsibility to produce the annual reports as required.

The Chief Investigator will notify the REC of the end of the trial.

If the trial is ended prematurely, the Chief Investigator will notify the REC, including the reasons for the premature termination.

ISRCTN: 64639614 IRAS: 313485 CPMS: 53277

Within one year after the end of the trial, the Chief Investigator will submit a final report with the results, including any publications/abstracts, to the REC.

#### 13.2 Peer Review

The protocol has been reviewed by 2 independent experts who will chair the TSC and DMC. The trial design has also been through an RfPB application process, during which it has been reviewed by a number of experts assessing research proposals.

#### 13.3 Patient and Public Involvement

We have sought the views of patients with COPD requiring NIV on the planned research, including: a) the importance of the clinical question; b) the trial design and burden of the assessments; and c) willingness to participate. Patients have found the assessments manageable, and have contributed to layout design, instructions and terminology used on the assessments.

The Northumbria Lung Research PPI COPD Group (NLRPG) have met twice in person to review this trial, the assessments required and all patient-facing documents. They will continue to meet regularly to discuss this trial, supported by our PPI lead, who will attend and feedback to the TMG, and assist the PPI group with dissemination of results. In response to feedback from the NLRPG, we will produce a video of a clinician reading the full patient information sheet as an alternative option of providing information about the study prior to consent. The NLRPG have also provided input into layout of modifiable assessments used in the trial design and have supported the importance of including the assessments asked during the acute phase. In particular, assessing quality of sleep as an outcome was highly important to the group.

In addition, real-time patient experience capture (following primary outcome) will inform our research. PPI activities will include: a) co-design of a PPI impact log to capture and evaluate the impact of PPI activities; b) ensuring study materials are appropriate for all potential participants by removing any equality, diversity and inclusion barriers; c) measurement of patient experience and thematic analysis of results for integration into trial results; and d) co-creation of a dissemination plan, and dissemination of results and PPI impact results to trial participants and people with COPD. Our patient research experience surveys to inform future PPI and trial conduct.

#### 13.4 Regulatory Compliance

The trial will not commence until a favourable REC opinion and HRA approval have been obtained. The anticipated start date for recruitment is 1st September 2022.

## 13.5 Protocol Compliance

A study related deviation is a departure from the ethically approved study protocol or other study document or process (e.g. consent process or administration of study intervention) or from Good Clinical Practice (GCP) or any applicable regulatory requirements. Any deviations from the protocol will be reported to the CI, documented in a protocol deviation form, and filed in the study master file.

## 13.6 Notification of Serious Breaches to GCP and/or the Protocol

The CI will be notified immediately of any case where the above definition applies during the trial conduct phase.

ISRCTN: 64639614 IRAS: 313485 CPMS: 53277

#### 13.7 Data Protection and Patient Confidentiality

Participant's personal identifying information will be replaced with an unrelated sequence of characters, with the data and the linking code secured in separate locations. Access to data will be limited to a need only basis. All electronic data will be transferred via the secure database, stored for at least 3 years after the end of the trial, and owned by the CI and R&D department (Northumbria Healthcare).

# 13.8 Financial and other competing interests for the Chief Investigator, PIs at each Site and Committee members for the overall Trial Management

Funding has been provided independently by NIHR (RfPB).

#### 13.9 Indemnity

Northumbria Healthcare NHS Trust has liability for clinical negligence. NHS Indemnity covers NHS staff and medical academic staff with honorary contracts for potential liability in respect of negligent harm arising from the conduct of the trial.

As Sponsor, Northumbria Healthcare NHS Foundation Trust will provide indemnity in respect of potential liability and negligent harm arising from trial management.

Indemnity in respect of potential liability arising from negligent harm related to trial design is provided by Northumbria Healthcare NHS Foundation Trust.

This is a non-commercial trial and therefore there are no arrangements for non-negligent compensation.

#### 13.10 Amendments

Following Sponsor approval, the protocol, informed consent form, and participant information sheet will be submitted to an appropriate Research Ethics Committee (REC), and HRA (where required) and host institutions for written approval.

The Investigator will submit and, where necessary, obtain approval from the above parties for all substantial amendments to the original approved documents.

All amendments must be discussed with the Chief Investigator, and an amendment history will be recorded. The most up to date protocol version will be available to all sites.

#### 13.11 Post Trial Care

The CI will ensure that this study is conducted in accordance with relevant regulations and with Good Clinical Practice, and with the principles of the Declaration of Helsinki.

#### 13.12 Access to the Final Trial Dataset

The CI, Host Organisation, Statistician and Health Economist will have access to the full dataset, for the duration of the trial.

ISRCTN: 64639614 IRAS: 313485 CPMS: 53277

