### 4. Trial Design

A multi-centre, open-label, parallel, randomised controlled trial.

Our position is one of equipoise. The randomised controlled trial design will provide a definitive result as to the better outcome for patients: a) a standard wean may provide a longer duration of NIV wean, with lower PaCO2 at discharge, with less relapse and readmissions; or b) an accelerated wean may mean a shorter duration of NIV wean, but with more relapse requiring NIV, and more readmissions.

IRAS: 313485 CPMS: 53277

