#### 5. Trial Setting

Patients will be recruited from at least seven secondary care centres across the UK, with different structures of care, to ensure that the results are applicable across the NHS. The centres have been carefully selected, based on current standard weaning time from acute NIV, and with PIs for each site confirming their commitment to adhere to the weaning protocols.

Confirmed recruiting sites are: 1) Northumbria Healthcare NHS Foundation Trust; 2) Newcastle Upon Tyne NHS Foundation Trust; 3) North Tees and Hartlepool NHS Foundation Trust; 4) The Leeds Teaching Hospitals NHS Trust; 5) Royal United Hospitals Bath NHS Foundation Trust; 6) University Hospitals Plymouth NHS Trust; 7) Nottingham University Hospitals NHS Trust; and 8) University Hospitals of Leicester NHS Trust.

Patients requiring NIV are managed on critical care or respiratory support units, and will be identified by daily screening by the usual care team.

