#### 7.4 Blinding

As this is an interventional RCT comparing two weaning strategies, usual care clinicians and participants cannot be blinded to the trial. However, patient identifiable data will not be visible to the lead site (Northumbria Healthcare). All data collected will be anonymised to the statistician and health economist for the purpose of analysis.

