#### 7.6 Baseline Data

A separate source document worksheet (collecting the following data) and manual will be provided to all participating sites. The case report form is electronic (REDCap). Key data are shown in Table 1.

Table 1. Key data for source document worksheet.

Category	Data
Patient demographics	Name; NHS number. Hospital number; Gender; Age; Ethnicity; Multiple index of deprivation decile; Recruiting Site, Participant identifier generated at randomisation.
COPD diagnosis	Previous spirometry; Discharge spirometry (if required); Exacerbation history; NIV history; LTOT prescription; Covid-19 history; Previous lung surgery.
Admission indices	Date and time of arrival at hospital; Date and time clinician contacted to start NIV; Date and time NIV mask applied; Where NIV started and continued; Date and time patient moved to dedicated NIV area; Observations on arrival; Chest x-ray changes; ECG; Date and time of discharge from hospital; Mortality.
Risk stratification	NIV Outcomes score; eMRCD; DECAF; Apache II score; Charlson index.
Blood results	Full blood count indices.
Past Medical History	Various cardiovascular, respiratory and immunodeficiency variables.
Medication history	Bronchodilators, cardiovascular and antibiotic medications.
Social history	Home circumstances; smoking history; employment; Rockwood clinical frailty score; baseline function.
Blood gases	pH; PaCO 2 ; PaO 2 ; HCO 3 -; BE; SaO 2 .
NIV data	IPAP; EPAP/PEEP/CPAP; PS; Back up rate; Respiratory rate; Tidal volumes; Minute ventilation; Patient trigger, Interface used, Weaning plan; Complications; Date and time NIV removed; Relapse.

ISRCTN: 64639614 IRAS: 313485 CPMS: 53277

Observations	SpO2; Blood pressure; Heart rate; Temperature.
Randomisation	Standard weaning protocol; accelerated weaning protocol.
allocation	
Patient	Borg breathless scale; Phlegm visual analogue scale; Richards-
reported	Campbell sleep questionnaire; Hospital Anxiety and Depression scale; St
outcome	Georges Respiratory Questionnaire (COPD); EQ-5D-5L.
measures	
Trial outcomes	Readmissions; Mortality; Health economics (GP attendances;
	Emergency Department attendances; Readmission to hospital).

Respiratory Rate: **count** the number of breaths observed in 1 minute.

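### Section 13.12 gives the trial team the full dataset while the trial is running, and nothing in the protocol keeps accumulating outcomes by arm from those running it

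*Protocol*

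**What the plan says.** Section 13.12 (Access to the Final Trial Dataset) consists of one sentence: "The CI, Host Organisation, Statistician and Health Economist will have access to the full dataset, for the duration of the trial".

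Section 4 describes the design: "A multi-centre, open-label, parallel, randomised controlled trial". Section 7.4 accepts that "usual care clinicians and participants cannot be blinded to the trial". For the analysts it adds: "All data collected will be anonymised to the statistician and health economist for the purpose of analysis". Section 11.2 gives participants a trial code "so that name and identifying data will be blinded to the statistician and health economist".

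Section 10.6 says "No routine interim analysis is planned". If survival comes to differ substantially, the DMC may consider a survival analysis, with a Haybittle-Peto threshold of p<0.001 guiding any decision to stop.

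**The concern.** The heading and the text of section 13.12 do not fit together. The heading suggests release once the data are complete, but the sentence covers the period in which patients are still being recruited, weaned and followed up. Read as written, the people who run the trial may hold outcomes together with allocation throughout.

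This matters more here than in a blinded trial with a fixed laboratory endpoint. Time to successful weaning depends on when unblinded clinicians move a patient through the steps and on whether NIV is restarted within 48 hours. A team that knows how the arms are running could, without intending to, change how it weans, recruits or advises sites, or how it settles analysis choices. Such influence would be hard to detect or exclude afterwards.

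**Working it through.** No figure in the protocol attaches to this point, so the check is a comparison of sections.

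1. **When access applies.** Section 13.12 grants it during the trial. Section 10.1 puts that at 27 months from first visit to last, which agrees with 24 months of recruitment plus 90 days of follow-up. No section delays access until database lock.

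2. **What the dataset holds.** Table 1 in section 7.6 lists the randomisation allocation ("Standard weaning protocol; accelerated weaning protocol") with the date and time NIV was removed, relapse, mortality and readmissions. The arm and the outcomes sit in the same data.

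3. **What is hidden.** Table 1 also lists name and NHS number. Sections 7.4 and 11.2 withhold identifying data from the lead site, the statistician and the health economist, so the full dataset of section 13.12 is already qualified for identity. No section qualifies it for allocation, and removing a name does not hide an arm.

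4. **Who receives it.** Under section vi the chief investigator chairs the Trial Management Group and carries primary responsibility for design, conduct and reporting. The host organisation heads the list in section 5: "Confirmed recruiting sites are: 1) Northumbria Healthcare NHS Foundation Trust", one of eight named sites. Under section 14.2 the chief investigator and the host write the publications.

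5. **What is reserved for the DMC.** Section vi requires its members to have no part in running the trial. Section 10.6 gives it the decision on any interim survival analysis. The protocol provides for no interim comparison of weaning time by anyone. Nothing in section 13.12 carries this separation over to data access.

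6. **Where knowledge of a trend could act.** In the standard arm (section 8.1), several steps may be taken in one day and a blood gas may be skipped on clinical judgement. In the accelerated arm (section 8.2), clinical concern can prompt an additional blood gas. In both arms, restarting NIV within 48 hours changes the endpoint. On the analysis side, section 10.3.2 adjusts for predictors not named in the protocol, and section 10.4 makes all subgroup analyses post hoc. A statistical analysis plan may settle those choices; what matters is that they are settled before its authors see results by arm.

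7. **Which access is needed.** Section 12 requires verification of eligibility and of all primary and secondary outcomes, and lets the chief investigator review allocation and adherence. Adherence to an arm-specific protocol cannot be checked without knowing the arm. The endpoint is also timed differently: at the last mask removal in the standard arm (section 8.1), and at the blood gas confirming the first successful four-hour trial in the accelerated arm (section 8.2). Record-level checks therefore need the allocation field. What they do not need is outcomes aggregated and compared by arm. The line belongs there.

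**The case against.** The strongest reply is that section 13.12 is a loosely worded access clause. Its heading points to the final data, it does not say that anyone will tabulate outcomes by arm, and sections 7.4 and 11.2 already limit it. The DMC keeps its independent chair, its uninvolved members and its reporting line to the steering committee; access to records neither performs the survival analysis of section 10.6 nor moves its threshold. Several decisions are also constrained. Restarting NIV after an accelerated trial follows a pH criterion (section 8.2), failure to wean requires recurrent AHRF needing NIV (section 3.3), site expansion is tied to recruitment concerns (section 10.2), and recruitment ends at 164 (section 7.12). Clinicians know their own patients' arms in any case.

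Much of this stands, and it limits the point. It does not remove it. The operative words still cover the running trial, the existing limits concern identity only, and discretion remains, chiefly over the timing of standard-arm steps. Knowing one's own patients' arms is also different from seeing the accumulating difference across all sites.

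A reader might go further and infer that section 10.6 is emptied of meaning, or that the false-positive rate is inflated as it would be by repeated significance testing. The protocol supports neither. It plans no repeated tests of the primary outcome, and a repeated-testing calculation describes declaring success at one of several looks, which is a different mechanism from conduct drifting because a trend is known.

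**Conclusion.** The point holds as a gap in access control. Section 13.12 as worded lets those running an open-label trial see accumulating outcomes by arm, and no other section prevents it. This is an avoidable risk of bias in conduct and analysis; the protocol gives no evidence that the arms will be compared early or that bias has occurred.

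The size of any bias cannot be computed from the document, and no number should be put on it. The exposure is up to 164 participants over the planned 27 months. The conclusion assumes that the sentence means what it says. If release after lock was intended, the heading is right and the sentence is wrong, and the same edit repairs it. The sample size is not affected. This is a cheap improvement rather than a flaw that threatens the trial.

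**What to change.** Replace the sentence in section 13.12 with:

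> Until database lock, outcome data summarised or compared by allocation are seen only by the DMC and the statistician preparing its closed reports. The CI, host organisation and health economist have record-level access only as needed for monitoring, data verification and safety (section 12), and otherwise see pooled summaries. The full dataset is released to them after lock.

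Mirror this in section 7.4, which at present speaks only of anonymisation. Finalise the analysis plan before any by-arm outcome summary is produced for those writing it. If the trial statistician also prepares the DMC's reports, that means before the first such report.

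Masking the arm throughout would not work, because the record-level checks need it and the weaning data would reveal it. The proposed text leaves the allocation field available for those checks.

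The cost is the protocol wording and tighter export and report rights in REDCap, which section 11.2 says already has levels of access for sites. The lead team would have no by-arm summaries before lock. No extra staff are needed.
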